6.1.11 PK Blood Samples

On Week 0, blood will be drawn for UBX0101 plasma concentrations at 2 hours postdose with a ±15-minute window.

Samples must be collected, processed, and shipped in accordance with the instructions in the Laboratory Manual.

6.1.12 Biomarkers: Blood and Urine

The Laboratory Manual contains detailed instructions for the collection and preparation of samples, directions with respect to the utilization of specialized tubes and requirements for dispensing of aliquots, and storage and shipment of samples to the Sponsor's nominated central laboratory.

6.1.12.1 Blood Collection for Biomarker Analysis

Whole blood to yield plasma and serum samples will be collected per standard of care and will be processed and shipped according to instructions provided in the Laboratory Manual.

6.1.12.2 Urine Collection for Biomarker Analysis

Samples must not be from the first morning void. Urine biomarker sample collection, processing, and shipping instructions can be found in the Laboratory Manual.

6.1.13 Imaging Biomarkers

MRI scans and fixed flexion, standing radiographs of the knee will be obtained at Screening and the Final Follow-up (Visit 8/Week 24) and used to perform exploratory biomarker analyses. Acquisition parameters, transmission instructions, reading, and analyses will be stipulated in the Imaging Manual and/or Imaging Charter.

The imaging sites will be qualified to ensure research conversance and suitability of facilities. The imaging site personnel will be trained by imaging experts prior to initiation of the study. Imaging data will be redacted to ensure that patient identifiers are removed, and the image will be transmitted to a core imaging laboratory, stored in a central imaging database for the study and assessed by central expert reader(s).

6.1.14 End of Study

The study will be considered complete when the last patient has completed the last study visit.

6.2 Discontinuation or Withdrawal

6.2.1 Individual Patients

6.2.1.1 Withdrawal from Study

Patients can voluntarily withdraw from the study for any reason at any time. They are to be considered withdrawn if they state an intention to withdraw, fail to return for visits, or become lost to follow-up for any reason. Patients withdrawing from the study because of an AE should be followed for at least 30 days, until resolution of the AE, or until no further improvement is expected, whichever comes first. Patients withdrawing from the study should be encouraged to complete all assessments under the Unscheduled/Early Termination visit described in Table 1.

6.2.1.2 Replacement of Patients

Patients who drop out of the study prior to the data cutoff for the primary endpoint will not be replaced.

6.3 Study Termination

The Sponsor may suspend or terminate the study or any part of the study at any time for any reason. If the Investigator suspends or terminates that site's participation in the study, the Investigator will promptly inform the Sponsor and the IRB/IEC and provide a detailed written explanation. Upon study completion, the Investigator will provide the Sponsor with final reports and summaries as required by regulations. Upon study suspension, completion, or termination, the Investigator will return all Study Drug, ePRO devices, and other study materials to the Sponsor or designee or destroy the materials at the investigative site per the Sponsor's instructions.

7 STUDY INTERVENTIONS

7.1 Description of Products

The Study Drugs (UBX0101 and placebo) to be provided to the clinical sites will be bulk packaged (sites will be supplied with adequate overage, which will be accounted for as part of Study Drug accountability). The term "Study Drug" when used throughout this protocol means UBX0101 in solution or placebo. Each vial and carton will be individually labeled. Study Drug labeling will include identification required by local law, drug identification, and dosage. The packaging and labeling of the Study Drug will be in accordance with the Sponsor's standards and local regulations. The Study Drugs are manufactured by Vetter Development Service.

7.1.1 UBX0101

7.1.1.1 Formulation, Storage, Preparation, and Handling

The Study Drug will be prepared by an unblinded pharmacist in accordance with the Pharmacy Manual. One or more qualified injectors (e.g., Principal Investigator or Sub-Investigator) will be designated at the site. The injectors will remain blinded. The unblinded pharmacist will not be permitted to interact with patients or conduct any study assessments. Full guidance for Study Drug preparation and administration will be given in the Pharmacy Manual. Documentation of this administration will be retained in the site file and will also be recorded in the eCRFs.

Storage and Accountability

UBX0101 0.5 mg/mL is formulated as a sterile "index solution" at a concentration of 0.5 mg/mL solution in phosphate-buffered saline with 0.4% Polysorbate 80, pH 7.4. Each vial contains 0.5 mg/mL of UBX0101 and is suitable for single-use only. UBX0101 should be stored at -20°C upon receipt. See further details in the UBX0101 Investigator's Brochure (IB).

Storage and dose preparation of study drug will be conducted in accordance with instructions in the Pharmacy Manual and under aseptic conditions.

The Investigator is responsible for drug accountability at the investigational site, appointing a qualified individual to oversee the storage, preparation, and dispensing of Study Drug, and keeping records of such activity in accordance with the requirements of the Sponsor.

All used and unused Study Drug must be stored at site and stored in accordance with the directions given in the Pharmacy Manual.

7.1.1.2 Dosing and Administration

Study Drug will be provided to the responsible pharmacist at the investigational site along with a Pharmacy Manual, which details clinical product presentation and dilutions to be prepared under aseptic conditions.

UBX0101 will be provided in sterile glass vials. Sterile diluent (phosphate-buffered saline with 0.4% Polysorbate 80, pH 7.4) will be provided along with sterile syringes and sterile needles for the preparation of the Study Drug. The Study Drug will be prepared by the unblinded pharmacist based on the patient's treatment allocation as assigned in the randomization system and according to the Pharmacy Manual.

The Study Drug, UBX0101, is administered under ultrasound guidance as a single IA injection in a total volume of 8 mL and will be administered using the following regimens based on treatment group assignment:

Group 2: UBX0101 0.5 mg IA at Week 0

Group 3: UBX0101 2.0 mg IA at Week 0

Group 4: UBX0101 4.0 mg IA at Week 0

7.1.2 Placebo – Phosphate-Buffered Saline

7.1.2.1 Formulation, Storage, Preparation, and Handling

Placebo is the same as the diluent and will be provided as a sterile solution of phosphate-buffered saline with 0.4% Polysorbate 80, pH 7.4, in 10 mL glass vials (see Section 7.1.1.1).

7.1.2.2 Dosing and Administration

The placebo is administered under ultrasound guidance as a single 8 mL IA injection and will be administered using the following regimen based on treatment group assignment:

Group 1: Placebo IA at Week 0

7.2 Treatment Assignment and Bias Minimization

7.2.1 Treatment Allocation

This study will be double-blind and placebo-controlled; the Investigators, study personnel, and patients will be blinded to the treatment assignment. A designated site pharmacist will be unblinded in order to prepare the Study Drug and placebo for administration. The site pharmacist will have access to the treatment allocation through a specialized role within the randomization system, which has role-based permissions. Procedures for maintaining the blind are covered in Section 7.2.3.

7.2.2 Randomization Strategy and Procedure

Patients will be randomly allocated to receive treatment through the randomization system, which administers the randomization code generated by the Sponsor's biostatistician or designee.

A randomization schedule will determine the allocation of either active Study Drug or placebo for each patient by group. Patients randomized to the placebo group (Group 1) will receive a single placebo IA injection at Week 0. Patients in Group 2 will receive a single 0.5 mg IA injection of UBX0101 at Week 0, patients in Group 3 will receive a single 2.0 mg IA injection of UBX0101 at Week 0, and patients in Group 4 will receive a single 4.0 mg IA injection of UBX0101 at Week 0 (Figure 1). Each injection will be a total of 8 mL.

7.2.3 Extent and Maintenance of Blinding

This study will be double-blind; Investigator and Patient will be blind to the treatment assigned. However, the site pharmacist will be required to prepare Study Drug and will therefore have knowledge of the treatment code; the site pharmacist is otherwise not involved in any study

procedures. Sponsor personnel or any designee who is actively engaged with the site will remain blinded.

Treatment will be prepared and dispensed by the unblinded site pharmacist in accordance with the randomization schedule provided by the Sponsor and administered electronically through the randomization system. The site pharmacist may not be involved with the study procedures, assessments, or data recording and will not reveal the randomization code to anyone. The Study Drug will be administered to the target knee through IA injection by an appropriately qualified blinded injector (this individual may be the Investigator or a nominated Sub-Investigator) in the clinic.

It is of importance to ensure that patients are blind to the treatment received; it is recognized that the method of administration of IA injection has the propensity to contribute to a placebo response (Altman et al. 2016), and therefore, maintaining the blind for patients, Investigators, and study personnel who assess patients will assist in minimizing this bias.

7.2.4 Unblinding Procedures

7.2.4.1 Planned Unblinding

Not applicable

7.2.4.2 Unplanned or Unintentional Unblinding

The randomization system will be used to manage roles and permissions with respect to the ability to break the blind. If the Investigator must know immediately what treatment the patient received in order to provide adequate medical care, the code for that patient may be obtained by breaking the blind in the randomization system, which will require recording of the reason for unblinding the treatment allocation.

The Investigator must contact the Medical Monitor to discuss any need to unblind the treatment allocation for a patient in the study prior to unblinding, unless medical emergency dictates otherwise. The randomization code and records regarding any unblinding events will form part of the essential study documents.

A patient who has unplanned or unintentional unblinding during the study will be asked to continue in the study through Week 24 for safety follow-up (AE and concomitant medication reporting, vital signs, physical examinations, and laboratory testing) as well as urine/serum biomarker specimen collections and knee imaging. Patient-reported data will be excluded from efficacy analyses from the point of unblinding onward.

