3 OBJECTIVES AND ENDPOINTS

Objectives and endpoints for this study are listed in Table 2.

 Table 2
 Study Objectives and Endpoints

Tier	Objectives	Endpoints
Primary	Evaluate the effect of IA administration of UBX0101 on the change from baseline to Week 12 of pain in the target knee	Change from baseline to Week 12 of the WOMAC-A score in patients receiving a single 0.5, 2.0, or 4.0 mg dose of UBX0101 versus those receiving placebo
Secondary	Evaluate the effect of IA administration of UBX0101 on the change from baseline to Week 12 in physical function	Change from baseline to Week 12 of the WOMAC-C function subscale score in patients receiving a single 0.5, 2.0, or 4.0 mg dose of UBX0101 versus those receiving placebo
Secondary	Evaluate the effect of IA administration of UBX0101 on the change from baseline to Week 12 in pain reported by patients daily over the 12-week study period	Change from baseline to Week 12 of the weekly mean of the average daily pain intensity scores on the 11-point NRS in patients receiving a single 0.5, 2.0, or 4.0 mg dose of UBX0101 versus those receiving placebo
Secondary	Evaluate the effect of IA administration of UBX0101 on the duration of symptom improvement (pain and function) following IA administration of UBX0101 out to 24 weeks	Change from baseline (over the entire 24-week period, including both the primary study period and the 12-week follow-up period) out to Week 24 for the WOMAC-A, NRS, and WOMAC-C scores in Patients receiving a single 0.5, 2.0, or 4.0 mg dose of UBX0101 versus those receiving placebo
Secondary	Evaluate the safety and tolerability of single-dose IA administration of UBX0101	Incidence of AEs as well as change from baseline through Weeks 12 and 24 in vital signs and selected laboratory safety parameters (as deemed clinically appropriate) in patients receiving a single 0.5, 2.0, or 4.0 mg dose of UBX0101 versus those receiving placebo
Exploratory	Explore the effects of single-dose IA administration of UBX0101 on the change from baseline in patient reported assessment of their osteoarthritis at the time of inquiry	Change from baseline to Week 12 and to Week 24 in PGA score in patients receiving a single 0.5, 2.0, or 4.0 mg dose of UBX0101 versus those receiving placebo

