9.1.2.3 Intent-to-Treat Population

All patients who are randomized will be included in the Intent-to-Treat (ITT) population, and their data will be included in efficacy and exploratory data sets. Full reporting of deviations from randomization, noncompliance with study procedures, and protocol deviations will be captured. Data from the ITT population may be used to better understand the prognostic balance of the randomized population and if noncompliance or dropout from the study may be related to their treatment assignment and/or response to treatment.

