9.1.2.4 Modified Intent-to-Treat Population

The Modified-Intent-to Treat (mITT) population is a subset of the ITT population who have been randomized and treated. Patients in the mITT population and their data will be included in the safety as well as the efficacy and exploratory data sets.

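### Section 7.2.4.2 drops all patient-reported efficacy data after any unplanned unblinding, which conflicts with the ITT and mITT definitions and can remove Week 12 primary values

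*Combined protocol and SAP*

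**What the plan says.** Section 7.2.4.2 covers emergency code breaks and accidental disclosure together. The one reason it describes for breaking the code is clinical: "If the Investigator must know immediately what treatment the patient received in order to provide adequate medical care". It then sets out what happens next: "A patient who has unplanned or unintentional unblinding during the study will be asked to continue in the study through Week 24 for safety follow-up". The list that follows names adverse events, concomitant medication, vital signs, examinations, laboratory tests, biomarker samples and knee imaging. No patient-reported instrument is on it. The section ends with the analysis rule: "Patient-reported data will be excluded from efficacy analyses from the point of unblinding onward".

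The population definitions carry no matching exception. For all randomised patients, Section 9.1.2.3 says "their data will be included in efficacy and exploratory data sets". For randomised and treated patients, Section 9.1.2.4 says "Patients in the mITT population and their data will be included in the safety as well as the efficacy and exploratory data sets".

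The primary endpoint in Section 3 is "Change from baseline to Week 12 of the WOMAC-A score", and Section 6.1.9 lists WOMAC among the patient-reported outcomes. Section 9.1.3 leaves the efficacy analysis to the Statistical Analysis Plan. The text available for this review contains no estimand, missing-data method or sensitivity analysis for these exclusions.

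**The concern.** Three features of the rule matter together.

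- **It is set off by something that happens after randomisation.** A need for medical care can depend on dose or on how the knee is doing. Dropping outcomes for that reason makes the missing data potentially informative. The drug is a single Day 1 injection (Section 4.1), so later unblinding does not change the treatment received.
- **It reaches the primary endpoint.** If unblinding comes before the Week 12 assessment, that patient's Week 12 WOMAC-A value leaves the efficacy analysis.
- **It is wider than its purpose.** Section 7.2.3 is concerned with expectation bias in patients and assessors. The exclusion makes no distinction by who learned the allocation, so on its face it also covers a patient who is still blind after a code break seen only by the Investigator.

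The list of continuing assessments adds a practical risk. A site could read it as leave to stop WOMAC and the diary after unblinding.

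**Working it through.** **1. The sections side by side**

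| Section | Whose data | Exception for unblinding |
|---|---|---|
| 7.2.4.2 | Patients with unplanned or unintentional unblinding | Patient-reported data leave efficacy analyses from that point |
| 9.1.2.3 (ITT) | All randomised | None |
| 9.1.2.4 (mITT) | Randomised and treated | None |

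The protocol does not say whether ITT or mITT is primary. The conflict arises with either.

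**2. The plan's own sample size**

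Inputs from Section 9.1.1: difference 0.50 on the 0–4 item score, SD 0.75, two-sided alpha 0.10, power 90%, dropout 10%.

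n per arm = 2 × (1.645 + 1.282)² × 0.75² / 0.50² = 38.5, so 39 by the normal approximation. The noncentral t gives power 0.898 at 39 and 0.905 at 40, so 40 completers. 40 / 0.90 = 44.4, so 45 per arm and 180 in total. The plan's figures reproduce.

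**3. How many patients might be affected**

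The documents give no unblinding rate. The only rough proxy is serious adverse events in Phase 1, 0 of 78 (Section 2.1.3). The exact one-sided 95% upper bound is 1 − 0.05^(1/78) = 3.77%. That is 0.0377 × 180 = 6.8 patients in the trial, or 0.0377 × 45 = 1.7 per arm. Accidental unblinding is not captured by this proxy.

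**4. Shift in an arm mean**

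If k of 40 patients are dropped and their mean change differs by D from the rest, the arm mean moves by (k/40) × D. D is an assumption.

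| k of 40 | D = 0.5 | D = 1.0 |
|---|---|---|
| 1 | 0.0125 | 0.025 |
| 2 | 0.025 | 0.05 |
| 4 | 0.05 | 0.10 |

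For k = 2 the shift is 5% to 10% of the planned 0.50 effect (0.025/0.50 and 0.05/0.50).

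**5. Rejection rate with no true effect**

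SE = 0.75 × √(2/40) = 0.168. With 78 degrees of freedom the two-sided 10% critical value is 1.665, and the noncentrality is shift/SE.

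- Shift 0.025: noncentrality 0.149, rejection 10.4%.
- Shift 0.05: noncentrality 0.298, rejection 11.5%.
- Shift 0.10: noncentrality 0.596, rejection 15.9%.

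These assume losses in one arm of the comparison and none in the other. Using 38 instead of 40 in the affected arm changes 11.5% to 11.4%.

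**6. Power**

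By the normal approximation, losing 2 patients from both compared arms lowers power from 0.909 to 0.896. Precision is not the issue.

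**The case against.** The strongest defence is that a population definition says who is in the set, while Section 7.2.4.2 is a specific data rule for one rare event. The patient stays in the ITT population, baseline and earlier scores are kept, and a primary value is lost only if unblinding precedes Week 12. That is right, and it limits the consequences. The conflict remains, because both definitions include the patients' data as well as the patients, and neither points to an exception. The Statistical Analysis Plan may deal with the resulting gaps, but that cannot be checked here.

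A second defence is that a pain score given with knowledge of treatment is open to bias. This stands. A reader might go further than this point does and infer that the excluded ratings are sound and that dropping them removes no bias. The documents do not support that. Section 7.2.3 counts blinding of Investigators and assessing staff as protection against bias, and Appendix 3 has site staff ask the PGIC aloud. Staff who know the allocation could influence answers, even from a patient who is still blind. The objection is weaker for the e-diary NRS and the paper PGA, which the patient completes alone.

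A reader might also infer that collection stops, so that no sensitivity analysis could ever be run. Section 7.2.4.2 does not say so. Excluding data from analysis suggests that the data exist. Table 1 schedules WOMAC at every visit with no exemption, and its footnote 12 and Appendix 2 keep the daily NRS running to the end of participation. The text is ambiguous, and that is a reason to clarify it.

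**Conclusion.** The point holds as an inconsistency and as an avoidable, possibly informative loss of primary data. Section 7.2.4.2 does not agree with Sections 9.1.2.3 and 9.1.2.4, leaves continued collection unclear, and does not limit the exclusion to patients who know their allocation.

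The likely effect on the result is small: a shift of 0.025 to 0.05 in one arm mean, and a rejection rate of about 10.4% to 11.5% against 10%. This rests on 2 of 40 lost in one arm, none in the comparator, and an assumed difference of 0.5 to 1.0 point. Two of 40 (5%) is already slightly above the 3.77% proxy bound.

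The 15.9% figure should not be read as the expected size. It needs 4 of 40 lost in one arm only, which is 10% and about 2.7 times that bound, together with a full 1.0-point difference. Whether ratings made after the patient learned the allocation belong in the primary analysis is open to debate. What the plan needs is a stated choice, with both results shown.

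**What to change.** Amend Section 7.2.4.2 as follows, and align Sections 9.1.2.3 and 9.1.2.4 with it.

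1. State that all scheduled patient-reported assessments (WOMAC, NRS, PGA, PGIC) continue after unblinding.
2. Record who learned the allocation (patient, Investigator, site staff) and on what date. The section already requires the reason to be recorded and the unblinding records to be kept, so this adds two fields.
3. Keep in the ITT/mITT efficacy analysis at least the self-completed ratings of patients who are still blind. Say whether WOMAC counts as self-completed, since the protocol lists it as patient-reported but says only that it is administered at visits.
4. Report the primary endpoint with and without ratings made after the patient learned the allocation. Name in advance which version is primary, and how values are handled where ratings are left out.

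The cost is about one paragraph of amendment and one extra analysis. The downside is that a few ratings made after a code break enter an efficacy analysis. For patients who learned their allocation, the paired results show how much those ratings matter.

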7.3 Assessment and Verification of Compliance

The Study Drug will be managed by the unblinded pharmacist and verified at the investigational site by an unblinded clinical research associate (CRA) or an appropriately qualified designated member of the study team. A Pharmacy Manual will be supplied to the site, and all Study Drug will be required to be accounted for on appropriate drug accountability forms, which will be reviewed by an independent pharmacist. On preparation of the required dose for each patient, the pharmacist or designee will record the detail of vials utilized and retain the overage of the prepared solutions, if any.

7.4 Prior and Concomitant Therapies

7.4.1 Prohibited Therapies

Patients are prohibited from receiving any IA or topical treatment to the target knee during the course of the study, such as:

- IA viscosupplementation or steroid injections to either target or contralateral knee
- Topical NSAID
- Topical capsaicin
- · Lidocaine patch

Systemic treatments

- Oral corticosteroids for more than 2 weeks
- Except for tramadol, all other opioid analgesic use (such as oxycodone or codeine containing agents) up to 8 weeks prior to Screening and at all times during the study
- Other investigational drugs by any route of administration
- Anticoagulants (e.g., low molecular weight heparin or warfarin), factor Xa inhibitors (e.g., Eliquis®/apixaban), or P2Y12 inhibitors (e.g., clopidogrel, ticagrelor)

Alternative and non-pharmacological therapies that are prohibited during the course of the study include the following:

- Medical marijuana or marijuana-derived products
- Acupuncture in the target knee

